### 10.3 Vital Signs

Descriptive summaries of observed values and changes from baseline will be calculated for weight, temperature, systolic blood pressure, diastolic blood pressure, and pulse rate. These summaries will be presented by visit and treatment arm.

### 10.4 Electrocardiogram

The summary ECG assessment (categories: normal, abnormal – not clinically significant, abnormal – clinically significant) will be tabulated by visit (frequency tables). Additionally, shifts in assessments from baseline to EOS visit will be presented by treatment arm (shift tables).

Descriptive summaries of actual values and changes from baseline will be presented for ECG measures of PR interval, QRS interval, QT interval, QTc interval (Bazett), and HR (heart rate) by visit and treatment arm.

If not available in the clinical database, Bazett's Correction (QTcb) will be derived as follows:

$$\text{Bazett's Correction (QT}_{c_b}\text{)} \quad \text{QT}_{c_b} = \frac{QT_{msec}}{\sqrt{RR}}$$

where: Relative Rate:  $RR = 60 / \text{HR}$   
HR = heart rate obtained from ECG.

Also, the number and percentage of patients in each treatment group with QTc values 451 - 480 ms, 481 - 500 ms or >500 ms and the number and percentage of patients in each treatment group who experienced a change >30 ms or a change >60 ms will be presented by visit.

## 10.5 ECOG Performance Status

ECOG assessments will be tabulated by visit and treatment arm (frequency tables). Additionally, shifts in assessments from Baseline to EOS visit will be presented by treatment arm (shift tables). These analyses will be performed for the SAF population.

## 11. OTHER PLANNED ANALYSES

### 11.1 Comparison of Investigator and Centralized Tumor Response Assessments

Cross-tables comparing case-by-case the best overall investigator and centralized tumor response assessments (irRC) based on the entire treatment phase will be presented.

### 11.2 Anti-drug Antibodies

The incidence of ADAs will be summarized by sampling time point in frequency tables for the SAF population.

### 11.3 Hospitalization

Descriptive summaries of the percentage of days of hospitalization, based on the period between randomization and EOS, will be presented by treatment arm for the SAF population for all hospitalizations as well as broken down by reason.

### 11.4 Cytokines Release and Immune Cell Status

Cytokine release and immune cell counts (CD4+ T cells, CD8+ T cells, B cells, NK cells from FACS results and eosinophils, neutrophils and monocytes from blood count) analyses will include descriptive summaries of measured values and changes from baseline (absolute and percent changes, fold change for cytokines). All analyses will be performed by sampling time point and treatment arm for the respective subset of the ITT population. The time courses of cytokines and immune cell count will be displayed graphically (scatter plot overlaid by corresponding medians and interquartile ranges). The change of cytokines/serum factor from pre-first infusion to end of first infusion will be summarized by grades of timely related IRRs.

### 11.5 Pharmacokinetic Analysis

Derivation of pharmacokinetic parameters and statistical analyses will be performed by the xxxxxxxxxxxxxxxxxxxx Clinical Pharmacokinetics Department. Summaries of serum concentration data by sampling time point and derived PK parameters will be presented.

#### Serum Concentrations

For all patients treated with CetuGEXTM its concentration will be analyzed in serum samples.

For serum concentration data, all values below the limit of quantification (BLQ) will be set to BLQ/2 for summary statistics and graphs. Individual serum CetuGEXTM concentrations will be summarized at each time point using descriptive statistics. Individual concentration plots and mean data graphs will be produced. All graphs will be presented using both linear and semilogarithmic scales. All CetuGEXTM concentrations

will be presented in a by-subject listing.

#### Pharmacokinetic Parameters

Serum PK samples at pre-dose and at the end of each infusion will be collected from all patients. In addition, serum PK samples will be collected at 5 hours  $\pm$  5 min, 7 hours  $\pm$  15 min, 24 hours  $\pm$  1 hour, 48 hours  $\pm$  2 hours, 72 hours  $\pm$  2 hours and 168 hours  $\pm$  2 hours after the start of the 1st infusion on Day 1 from a subgroup of approximately 30 patients dosed with CetuGEX™. The same sampling regimen will also be taken after the 10th infusion. The resulting pharmacokinetic profiles obtained from this subgroup will be subjected to noncompartmental analysis, as data permit.

Pharmacokinetic parameter estimation will be performed using Phoenix WinNonlin® (Version 6.4 or later; Pharsight, Cary, NC) on individual serum concentration-time data. For the PK parameter calculation, BLQ serum concentrations occurring before Tmax will be set to BLQ/2 (50 ng/mL) with the exception of a BLQ value occurring between two measurable concentrations, in which case it will be set to missing. BLQ serum concentrations occurring after Tmax will be set to missing. Pharmacokinetic parameter estimates and summaries will be completed for subjects in the PK Population having sufficient measurable concentrations to define the profile. The calculation of terminal half-life will only be performed if at least three data points are available.

Pharmacokinetic parameter estimates, including Cmax, Cmin, Cavg, Tmax, MRT, AUC0-t, AUC0-∞, AUC%extrap, AUC0-tau, λz, t1/2, Vz, Vss, and CL, will be summarized using descriptive statistics, including arithmetic and geometric means, SD, %CV, median, minimum, and maximum. For Tmax, only the median and the range will be reported, as it is a categorical variable.

Values of AUC0-∞ for which the extrapolated part exceeded 20% will be flagged for possible exclusion from descriptive statistics.

The steady state will be assessed by visual observation of the mean trough (pre-dose) concentrations over time. Only trough concentrations for which the actual sampling time did not deviate by more than 2 hours from the nominal (planned) sampling time will be included in the steady state assessment. If the steady state is reached, mean accumulation ratio and fluctuation (%fluctuation) will also be calculated.

All pharmacokinetic calculations will be performed per WinNonlin standard noncompartmental algorithms, using actual sampling times elapsed from the start of the first infusion. Actual sampling times elapsed from the start of the 10th infusion will also be included in the PK input file

The correlation between PK parameters (AUC0-t, Cmax, Cmin, CL and t1/2) with body weight, body surface area and BMI will be explored in scatter plots and by calculating correlations coefficients.

#### **11.6 Quality of Life Analysis**

To assess the QoL of each patient, patient-reported disease-related symptoms and health related QoL will be measured using the EORTC-QLQ-C30 questionnaire and the head and neck module (H&N35; according to the availability of the validated translations).

The QoL questionnaires EORTC QLQ-C30 version 3.0 and QLQ-H&N35 are collected at Baseline and several post-baseline visits. The following scores will be derived:

- Global health status/QoL (revised): items 29 to 30

Functional scales (QLQ-C30)

- Physical functioning (revised): items 1 to 5
- Role functioning (revised): items 6 to 7
- Emotional functioning: items 21 to 24
- Cognitive functioning: items 20 and 25
- Social functioning: items 26 to 27

Symptom scales / items (QLQ-C30)

- Fatigue: items 10, 12, 18
- Nausea and vomiting: items 14, 15
- Pain: items 9, 19
- Dyspnea: item 8
- Insomnia: item 11
- Appetite loss: item 13
- Constipation: item 16
- Diarrhea: item 17
- Financial difficulties: item 28

Symptom scales / items (QLQ-H&N35)

- Pain: items 1 to 4
- Swallowing: items 5 to 8
- Senses problems: items 13 and 14
- Speech problems: items 16, 23 and 24
- Trouble with social eating: items 19 to 22
- Trouble with social contact: items 18 and 25 to 28
- Less sexuality: items 29 and 30
- Teeth: item 9
- Opening mouth: item 10
- Dry mouth: item 11
- Sticky saliva: item 12

- Coughing: item 15
- Felt ill: item 17
- Pain killers: item 31
- Nutritional supplements: item 32
- Feeding tube: item 33
- Weight loss: item 34
- Weight gain: item 35

Each of the scores will be derived individually if at least half of the required items are available. In general, the mean score will be derived first and then be linearly transformed in a way that 0 is the lowest and 100 is the highest possible value. Functional scores for QLQ-C30 will be reversed so that a value of 100 represents the highest level of functioning. Global and symptom scores will not be reversed so that 100 represents the highest possible QoL and the highest level of problems, respectively.

Summary statistics of all scores and their changes from baseline will be tabulated by cycle including p-values of a Wilcoxon rank test for the changes. The time courses of means scores will be presented as boxplots.

In addition, for the QLQ-C30 scales, the difference with respect to baseline will be classified as  $\leq -10$ ,  $-10 - 10$ ,  $\geq 10$ . The rates of patients within these ranges will be presented by treatment group and visit. The time from randomization to the first occurrence of a deterioration of at least 10 points ( $\leq -10$  for global and functional scales,  $\geq 10$  for symptom scales) will be analyzed by Kaplan-Meier methods. Patients without occurrence of deterioration will be censored at the last assessment. The estimate of the quartiles of the time to deterioration as well as the associated 95%-confidence intervals will be tabulated by treatment arm together with the p-value of a log rank test.

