6.2 Secondary Objectives

Secondary objectives are as follows:

1. To evaluate further efficacy criteria, safety and QoL of patients with stage III/IV recurrent and/or metastatic SCCHN treated with CetuGEX™ as compared to cetuximab (both in combination with platinum-based chemotherapy).
2. To assess PK parameters and profiles of CetuGEX™.
3. To assess efficacy and safety based on genetic markers for immune response (FcγR allotypes) and biomarkers.

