## **7. GENERAL ISSUES FOR STATISTICAL ANALYSIS**

### **7.1 General Statistical Methodology**

Descriptive summaries will be provided where appropriate for each of the study variables. In general, disposition summaries will be completed for all patients; summaries of protocol violations will be presented for the ITT population. Analyses of demography and baseline variables, and all efficacy analyses will be performed on the ITT and PP population. Safety and exposure analyses will be done on the SAF. All summaries will be presented for each treatment arm and for the total population, unless otherwise specified. Where data are collected over time, both the observed data and the change from baseline will be summarized at each visit.

Continuous variable summaries will include the number of patients with non-missing values (N), mean, standard deviation, median, minimum and maximum, 1st and 3rd quartile.

Categorical variable summaries will include the frequency and percentage of patients who are in the particular category. In general the denominator for the percentage calculation will be based upon the total number of patients in the study population for the treatment arm, unless otherwise specified.

Any patient who does not complete the study per protocol will be included in the analysis with the data available. Response and benefit rates will be based on the observed assessments and the number of patients in the respective population as the denominator, assuming no response/benefit for patients without sufficient data. Other imputation of missing values will not be performed, unless specified in the relevant sections of the SAP.

The last pre-administration observation will be used as the baseline value for calculating post-administration changes from baseline. All data obtained on the eCRF and entered into the database will be provided in separate data listings showing individual patient values.

Free text specifications (“other”) of multiple choice items will be detailed in the listings, in the tables the frequency of “other” will be displayed.

All analysis will be performed using SAS® Software version 9.3 or later.

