### **9.3.3 Correlation of Pharmacokinetic Parameters with PFS and CBR**

The following PK parameters of CetuGEX™ serum concentrations will be investigated concerning their impact on efficacy outcomes in the subgroup of patients who were treated with CetuGEX™

- Trough levels after 1st, 2nd and 3rd infusion (= pre-infusion concentrations at 2nd, 3rd and 4th infusion)
- Post-infusion concentration after 1st, 2nd and 3rd infusion.

Cox regression models including the PK parameter as continuous covariable will be fit to the primary PFS endpoint. Separate analyses will be performed for each of the 6 PK parameters. Hazard ratios, the corresponding 95%-confidence intervals and the p-values of the Wald test will be presented. A forest-plot will be provided to illustrate the hazard ratios and confidence interval for all 6 PK parameters in one figure.

Logistic regression models including the PK parameters as continuous covariable will be fitted to the CBR as assessed by the central review (RECIST). Separate analyses will be performed for each of the 6 PK parameters. Odds ratios, the corresponding 95%-confidence intervals and the p-values of the Wald test will be presented. Moreover, sample statistics of the PK parameters grouped by CB response (yes/no) will be presented including p-values of the Wilcoxon rank test. A forest-plot will be provided to illustrate the odd ratios and confidence interval for all 6 PK parameters in one figure.

These analyses will be based on PK population.

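### Quality of life is tested visit by visit on change from baseline among observed patients, with no baseline adjustment, no arm difference with a confidence interval, and no method for missing questionnaires

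*SAP*

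**What the plan says.** Comparing QoL between CetuGEX and cetuximab is a secondary objective (Protocol 6.2), and the QLQ-C30 and QLQ-H&N35 scores are secondary endpoints (SAP 2.2.1). Questionnaires are due at baseline, weeks 6, 12 and 18, and at the Safety Visit about four weeks after the last dose (Protocol 10.3.2).

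SAP 11.6 plans two kinds of comparison:

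- **All 33 scores.** Values and changes from baseline are "tabulated by cycle including p-values of a Wilcoxon rank test for the changes". No covariate, model, arm difference or confidence interval is named.
- **QLQ-C30 only.** Changes are classified at 10 points. Time to a first 10-point deterioration is analysed by Kaplan-Meier, with quartiles and their confidence intervals "tabulated by treatment arm together with the p-value of a log rank test". On censoring: "Patients without occurrence of deterioration will be censored at the last assessment".

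On missing data, SAP 7.1 says: "Any patient who does not complete the study per protocol will be included in the analysis with the data available". It adds: "Other imputation of missing values will not be performed, unless specified in the relevant sections of the SAP". Section 11.6 specifies nothing beyond the rule that a score needs at least half of its items.

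**The concern.** Three things are missing from the visit-wise analysis.

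- **Baseline adjustment.** Every patient should have a baseline value of the same score, usually the strongest available predictor of the later score. Subtracting it does not use it efficiently. SAP 9.1 and 9.2 give PFS, response, time to treatment failure and OS a supporting model with the stratification factors; QoL gets none.
- **An effect size.** A p-value alone does not tell the reader how far apart the arms are or how precisely that is known. For QLQ-H&N35, the disease-specific module, nothing else compares the arms.
- **A treatment of missing questionnaires.** The QoL tables are labelled ITT in SAP 15.1, but each test uses only patients with a score at that visit. If one arm keeps more patients on schedule, the two groups are selected to different degrees.

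At stake are the precision and readability of a secondary objective. The primary PFS test is not touched.

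**Working it through.** **Inputs from the documents.** Median PFS 5.6 and 8.4 months, 1:1 allocation, about 240 patients, two-sided 5%, 80% power (Protocol 13.2, SAP 5); QoL visits (Protocol 10.3.2); score list (SAP 11.6).

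**Input not in the documents.** The correlation r between baseline and follow-up scores. I assume 0.3 to 0.7 and also show 0.8 and 0.9.

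**1. The plan's own figure.** No power or sample size is stated for QoL, so the PFS calculation is the only one to reproduce. With HR = 5.6/8.4 = 0.667, Schoenfeld's formula gives 4(1.960 + 0.842)²/(ln 0.667)² = 191 events, against 192 planned. With 24 months of uniform accrual, 12 months of follow-up and 10% drop-out by the cut-off, the event probability is 0.808 and 192/0.808 = 238 patients, against about 240. The PFS medians are therefore a sound basis for step 4.

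**2. Scores and tests.** QLQ-C30 has 1 global, 5 functional and 9 symptom scores = 15. QLQ-H&N35 has 18. Total 33, of which 17 are single items (6 + 11) and 16 multi-item. Over four post-baseline visits, 33 × 4 = 132 p-values with no lead scale; at 5% under the null, 132 × 0.05 = 6.6 would be expected to fall below the threshold.

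**3. Precision.** Take equal variance σ² at baseline and follow-up.

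- Raw change: variance 2(1 − r)σ²
- Baseline-adjusted: variance (1 − r²)σ²
- Ratio, adjusted to raw: (1 + r)/2

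| r | ratio | variance reduction | extra patients needed by raw change, 2/(1 + r) − 1 |
|---|---|---|---|
| 0.3 | 0.65 | 35% | 54% |
| 0.5 | 0.75 | 25% | 33% |
| 0.7 | 0.85 | 15% | 18% |
| 0.8 | 0.90 | 10% | 11% |
| 0.9 | 0.95 | 5% | 5% |

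For normal data the rank test costs a further factor 3/π, which makes the loss 38%, 28% and 19% at r = 0.3, 0.5 and 0.7. In a simulation with 72 and 85 patients observed and an assumed difference of 0.4 SD (4,000 runs), power for r = 0.3, 0.5 and 0.7 was 54%, 68% and 88% for the rank-sum test on change, and 74%, 82% and 93% for baseline-adjusted analysis (ANCOVA).

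**4. Who is still on schedule.** Patients stay on the visit schedule until progression (Protocol 7.1.1). Under exponential PFS, the proportion progression-free at t months is 2^(−t/median).

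| Week | Months | Control | CetuGEX | Gap |
|---|---|---|---|---|
| 6 | 1.38 | 84% | 89% | 5 points |
| 12 | 2.76 | 71% | 80% | 9 points |
| 18 | 4.14 | 60% | 71% | 11 points |

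Of 120 per arm, that is about 72 and 85 at week 18. The questionnaire is completed before other assessments at a visit (Protocol 10.3.2), so a patient whose progression is first seen on the week-18 scan can still supply it. Attendance would then be nearer the week-12 row, about 85 and 96 of 120. These figures leave out withdrawal without progression. Under equal PFS the gap is zero.

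**5. Size of the selection bias.** Simulation with no QoL effect, 60% and 71% retained, r = 0.5 (4,000 runs):

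| Correlation of retention with week-18 QoL | Raw change: bias; type I error of Wilcoxon | Complete-case ANCOVA: bias; type I error |
|---|---|---|
| 0 | 0.00 SD; 4.5% | 0.00 SD; 5.0% |
| 0.3 | −0.03 SD; 5.7% | −0.04 SD; 5.7% |
| 0.6 | −0.05 SD; 6.0% | −0.08 SD; 8.7% |

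The bias is modest, and adjusting for baseline among completers does not remove it.

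**The case against.** The strongest reply is that QoL is an unpowered secondary endpoint in a phase II trial, that the SAP attaches no success claim to its p-values, and that SAP 11.6 already has a second between-arm analysis. A rank test is also a reasonable choice for the 17 single-item scores, where normal-theory variances fit poorly. All of this stands, and it limits the point to precision and reporting. The second analysis does not close the gap: it omits QLQ-H&N35, its censoring is open to the same selection, and it gives quartiles per arm but no arm contrast with an interval.

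Some stronger readings are tempting, but the documents do not support them:

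- **That the baseline score is thrown away.** Change from baseline uses it; it does not adjust for it. Under randomisation, chance baseline imbalance does not bias the comparison on average.
- **That 15% to 35% is a known cost.** It follows from an assumed r. The formula also compares normal-theory analyses, not the rank test itself.
- **That drop-out will be unequal.** No drop-out by arm is stated. The gap is inferred from the PFS design alternative. Patients who stop treatment without progression stay on schedule, and a Safety Visit questionnaire is planned.
- **That the Wilcoxon test is within arm.** SAP 11.6 does not say, but SAP 9.3.3 uses the same test name for a two-group comparison, "grouped by CB response (yes/no) will be presented including p-values of the Wilcoxon rank test", and SAP 10.1.3 does likewise. The two-sample reading is the likely one and needs only a clarifying word.
- **That omitting the strata is itself an error.** SAP 9.1 argues for an unstratified primary test. The gain claimed here comes mainly from the baseline score.

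**Conclusion.** The point holds as one of precision, reporting and unaddressed missing data. The visit-wise analysis leaves usable information aside and gives no arm difference with an interval; for QLQ-H&N35 it is the only between-arm analysis. The variance reduction from adjusting for baseline is 35% to 15% for r of 0.3 to 0.7, and 10% to 5% for r of 0.8 to 0.9. These figures rest on the assumed r and on equal variances over time.

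Selection is a secondary, conditional issue. It needs both a real PFS effect near the planned one and a link between staying on schedule and QoL. Even then, the simulated bias in change was about 0.03 to 0.05 SD. The change is worth making because it is cheap and serves a stated objective, not because the planned test is badly biased.

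**What to change.** Amend SAP 11.6 before database lock:

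1. **Multi-item scales (16).** Replace the per-visit Wilcoxon tests with a repeated-measures model for change at weeks 6, 12 and 18, with arm, visit, arm-by-visit, baseline score, baseline-by-visit and the four stratification factors. Enter the factors as main effects, so the 3 × 2 × 2 × 2 = 24 strata are not crossed. Report arm differences with 95% confidence intervals.
2. **Single-item scores (17).** Use a baseline-adjusted rank or ordinal analysis, and state that the comparison is between arms.
3. **Lead scale.** Name global health status/QoL and its week-18 arm difference as the leading result. Treat the other 32 scores as descriptive.
4. **Safety Visit.** Summarise it separately with baseline adjustment, because it falls at a different time since randomization for each patient.
5. **Missing data.** Report questionnaire completion by arm and visit, and add a sensitivity analysis for death and progression.
6. **Keep** the QLQ-C30 time-to-deterioration analysis.

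The cost is SAP wording and some extra programming on data already collected. The model is valid if data are missing at random given the observed scores and covariates. It does not remove bias if drop-out depends on unobserved QoL, which is why item 5 is needed.
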